D4i. Measurement of Child Engagement. Child engagement (i.e., general level of behavioral involvement with providers during treatment sessions) will be observationally rated by independent, trained coders via review of recorded sessions. The Child Involvement Ratings Scale (CIRS)^{21,103} will be used to code child engagement. Ten "child involvement" items – 6 positive, 4 negative – are rated for each session on a 6-point scale (i.e., "not at all" to "a great deal present"). The positive-involvement items emphasize the extent to which children initiate discussions, demonstrate enthusiasm, self-disclose, and demonstrate understanding. Items for negative involvement address withdrawal or avoidance in treatment. Coders will provide separate ratings for the first and second halves of each session, permitting observation of shifts in engagement within and across sessions. CIRS child engagement ratings have been associated with clinical outcomes²¹ and provider flexibility in delivery of EBPs.¹⁰⁴ Excellent internal consistency and interrater reliability were reported for the CIRS.^{21,104} Four independent raters were successfully trained to reliability in the pilot trial (ICC M=0.81; range: 0.60-1.00).

For this study, [name] will implement a training and reliability maintenance plan similar to that employed in the NIMH R34.⁴⁷ He will train four independent raters at MUSC to reliability in the CIRS and then lead bi-weekly maintenance calls to prevent rater drift as coders complete ratings. Initial reliability training will consist of a 2-day in-person didactic that reviews the CIRS manual and illustrates the individual items and scoring using “gold standard” recordings of TF-CBT that were developed in the R34. Coders will be considered reliable when they have achieved an ICC ≥ 0.60 on all 10 CIRS items compared to gold standard ratings.

D4j. Child Mental Health Measures at Baseline and 3-, 6-, 9-, and 12-month Post-Baseline Assessment

Measures that will be administered by televideo/phone to youth by independent study evaluators blind to condition:

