- Center for Epidemiologic Studies Depression Scale (CESD-R). The CESD-R is a 20-item self-report scale of depression. It is widely used and demonstrates excellent psychometric properties.¹¹⁸
- The Child and Adolescent Trauma Screen (CATS) – Caregiver Version is the 35-item parent version of the CATS-Youth.
- The Alabama Parenting Questionnaire (APQ; Frick, 1991) is a 42-item measure to assess parenting practices.
- The Kessler 6 (K6; Kessler et al., 2002) is a widely used 6-item measure of general distress that is well-validated.

D4l. Provider Practice Measures Administered at Study Entry and Completion

- We will measure Provider Characteristics and variables relevant to adoption of EBT, including caseload characteristics, age, race/ethnicity, and years of experience; this will be measured at study entry only.
- Evidence-Based Practice Attitude Scale (EBPAS)^{119,120} is 15 items, assessing providers’ perceptions of appeal of EBT, openness to innovation, perceived divergence with usual care (alphas .59-.90; M=.77).
- Knowledge of Behavioral Principles as Applied to Children (25 items) to assess understanding of the application of behavioral principles to youth. Internal consistency=.42-.84; sensitivity to change.¹²¹⁻¹²⁴
- Acceptability, Appropriateness and Feasibility Measure (Weiner et al., 2014) is a 12-item measure to monitor and evaluate implementation efforts. This measure has been shown to have solid psychometric properties.

- Computer Assisted Therapy Attitudes Scale (CATS, Becker & Jensen, 2013) is an 8-item measure design to assess attitudes toward computer use in treatment.
- Organizational Readiness for Implementing Change (ORIC; Shea et al., 2014) is a 12-item measure designed to assess an organization's readiness to implement new policies, programs, and practices.
- TF-CBT Organizational Support Measure is a 19-item instrument to assess a community mental health organization's activities related to the delivery of Trauma-Focused Cognitive-Behavioral Therapy (TF-CBT).
- Burnout. The Burnout measure is a two-item screener that assesses providers' feelings about their work, and their perceptions of how their co-workers feel about the work they do.

D8. Quantitative Data Analysis (Aim 2)

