D8a. Hypothesis 1: Higher levels of provider fidelity will be observed in tablet-facilitated vs. standard TF-CBT. To determine if the target of **provider fidelity** was affected by access to the tablet and tablet use, a 2-level MLM (level-1 child; level-2 provider) will be used. Fidelity will be measured by the TF CBT TPOCS-S. Fidelity scores will be calculated per child participant such that each provider will have 3 ratings. An aggregate score for the entire treatment of a case is consistent with prior use of these fidelity measures.¹³² An aggregate fidelity score will allow the hypothesis of differences across condition to be tested while accounting for nesting of multiple cases per provider. Similarly, this measurement lends itself to use as a mechanism of treatment response (Hypothesis 5). The level-1 model will include a fixed effect corresponding to the mean participant fidelity score with a random effect corresponding to variability across participants. The level-2 model will include a dichotomous fixed effect representing the condition to which each participant will be randomized (tablet-facilitated vs. standard TF-CBT). The inclusion of additional child (level-1) and provider (level-2) covariates will be evaluated by estimating changes in model fit according to the deviance statistic for nested models and the AIC/BIC for non-nested models.¹³⁰ Case order (1st-3rd) will be included as a level-1 fixed effect to examine the potential increase in fidelity across cases due to practice effects.

D8b. Hypothesis 2: Greater child engagement will be observed in tablet-facilitated vs. standard TF-CBT. A 2-level MLM (level-1 child; level-2 provider) will evaluate the effect of access to the tablet and tablet use on the target of **child engagement**. An aggregate CIRS score for each child will be used for the reasons described in Hypothesis 1. A prototypical level-1 model will include a fixed effect representing engagement scores for children at level 1. The level-2 model will include a dichotomous fixed effect representing the condition to which each child was randomized (tablet-facilitated vs. standard TF-CBT). The inclusion of additional child (level-1) and provider (level-2) covariates will be evaluated by estimating changes in model fit according to the deviance statistic for nested models and the AIC/BIC for non-nested models.¹³⁰ Case order (1st-3rd) will be included as a level-1 fixed effect to

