examine the potential increase in engagement across cases due to practice.

D8c. Hypothesis 3: Greater improvement in clinical outcomes will be observed at post-baseline assessments among children receiving tablet-facilitated TF-CBT vs. standard TF-CBT. Response to the intervention will be evaluated with a piecewise longitudinal MLM that contains 3 levels. Level-1 will correspond to measurement period, level-2 to child, and level-3 to provider. The primary outcome for Hypothesis 3 will be scores on the K-SADS-PL, UCLA PTSD Index, CDI, and CBCL. A piecewise model allows for separate change trajectories to be estimated for distinct periods of time. Patients are expected to show more rapid change during treatment than during follow-up (roughly corresponding to 9- and 12-month post-baseline period). The level-1 model will include a fixed effect for pretreatment (intercept), rate of change during treatment, and rate of change for the follow-up period. Time varying covariates (level-1) will be added to the model based on a theoretical rationale and changes in model fit. The level-2 model will account for child level covariates, including comorbid symptoms and trauma history. The level-3 model will include a dichotomous fixed effect representing the condition to which each provider was randomized (tablet-facilitated vs. standard TF-CBT). Of interest is the cross-level interaction between rate of change during treatment and the condition to which the provider was assigned. Cross-level interactions between the rate of change during follow-up also will be examined.

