The risks of this study phase are minimal from an experimental standpoint as study procedures closely follow those used in routine clinical care. Children and families receiving services using the tablet-based toolkit will be receiving these services from providers who have at their disposal resources designed to support the effective delivery of evidence-based treatment for their symptoms. It is anticipated that children and caregivers in this group will find the technology-based enhancements to treatment fun and engaging, consistent with reactions we observed in our pilot study, which may improve their treatment experience and their relationship with their providers. Providers in the proposed study will also benefit from their participation. Additionally, half, randomly selected, will receive training and access to a novel tablet-based application that is designed to assist them in increasing child engagement, structuring treatment sessions, implementing a treatment model with fidelity, reducing required time to prepare for sessions, and otherwise supporting their attempts to provide the best possible care to children and their families.

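### The covariate rules for Hypotheses 1 to 3 set no baseline limit, so the main models can adjust for follow-up measures that the toolkit may itself change

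*Protocol*

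**What the plan says.** **Hypothesis 3 (protocol D8c).** The level-1 rule is: "Time varying covariates (level-1) will be added to the model based on a theoretical rationale and changes in model fit". No such covariate is named. For the child level: "The level-2 model will account for child level covariates, including comorbid symptoms and trauma history". That gives two examples, an open list and no time of measurement. The effect of interest is the interaction of condition with the rate of change during treatment.

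**Hypotheses 1 and 2 (D8a, D8b).** "The inclusion of additional child (level-1) and provider (level-2) covariates will be evaluated by estimating changes in model fit", using the deviance for nested models and AIC/BIC otherwise. Case order is the only covariate fixed in advance. Both sections specify a two-level condition term.

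**SAP 2.9.1.** It has no covariate rule of its own beyond referring, as D8 does, to a cited textbook's guidelines for fixed and random effects.

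**Analysis set (D8g).** All eligible, enrolled cases are analysed. This settles who is analysed, not what is adjusted for.

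**What is measured, and when.** D4j is headed "Child Mental Health Measures at Baseline and 3-, 6-, 9-, and 12-month Post-Baseline Assessment" and lists 6 instruments. D4k puts 8 caregiver instruments on the same schedule. Four of these 14 measure alliance or satisfaction (TASC, CASQ, WAI, CSQ), and several are symptom scales. D4l is headed "Provider Practice Measures Administered at Study Entry and Completion"; of its 8 measures, only provider characteristics carry the note "this will be measured at study entry only".

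**Expected action of the toolkit (E.3).** Families may find it engaging, "which may improve their treatment experience and their relationship with their providers".

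**The concern.** Randomisation protects the comparison of conditions as long as the model adjusts only for things the toolkit cannot have changed. At follow-up visits a time-varying covariate takes values recorded after treatment has begun. If the toolkit moves that covariate, adjusting for it removes the part of the effect that runs through it. If the covariate and the outcome also share other causes, adjustment can create a difference where none exists.

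D8c does more than leave a gap: it says such covariates will be added. An analyst who put follow-up depression or alliance scores into the PTSD model would be following the protocol, and could report the result as the intention-to-treat effect. Requiring a theoretical rationale is weak protection, because the theory of this trial is that the toolkit changes what happens in treatment.

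**Working it through.** The plan gives no figure for covariate adjustment, so there is none to reproduce. From D8h I use only 80% power at alpha 0.05, taken as two-sided because the sidedness is not stated.

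**1. Effect left after adjustment.** Standardise outcome and covariate and code both so that higher is better. Let the total toolkit effect be T, its effect on the covariate f x T, and the covariate's coefficient b. Then:

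adjusted effect = T - b x (f x T) = T x (1 - b x f)

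**2. Approximate power.** The adjusted residual SD is sqrt(1 - b^2), and 1.96 + 0.84 = 2.80, so:

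power = Phi(2.80 x (1 - b x f) / sqrt(1 - b^2) - 1.96)

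The documents give neither b nor f. These values are assumed:

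| b | f | effect left | power (80% unadjusted) |
|---|---|---|---|
| 0.3 | 0 | 100% | 84% |
| 0.3 | 0.5 | 85% | 70% |
| 0.3 | 1 | 70% | 54% |
| 0.5 | 0 | 100% | 90% |
| 0.5 | 0.5 | 75% | 68% |
| 0.5 | 1 | 50% | 37% |

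Example: b = 0.3, f = 1 gives 2.80 x 0.70 / 0.954 - 1.96 = 0.09, and Phi(0.09) = 0.54.

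Power breaks even at f = (1 - sqrt(1 - b^2)) / b, which is 0.15 for b = 0.3 and 0.27 for b = 0.5. Below that, adjustment raises power; above it, adjustment lowers it.

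**3. Check in the Hypothesis 3 model.** Simulation with 120 providers x 3 children x 5 visits, a knot at 6 months, 600 trials per setting and three assumed provider/child/visit variance splits. Share left: 0.70-0.71 at (b, f) = (0.3, 1); 0.50-0.51 at (0.5, 1); 0.73-0.75 at (0.5, 0.5); 0.99-1.01 at (0.5, 0). The identity holds for the condition-by-slope term and does not depend on the split. Power was not simulated for this model.

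**4. Check in a two-level model, as for Hypotheses 1 and 2.** Simulation with 120 providers x 3 children, ICC 0.15 and a true effect of 0.34 SD; the covariate is kept only if the deviance falls by more than 3.84. The toolkit is assumed to shift the covariate by 0.54 SD.
- Covariate carrying 25% of the effect (b = 0.25 x 0.34 / 0.54 = 0.157): condition coefficient 0.26, power 56%.
- Covariate carrying 50% (b = 0.315): coefficient 0.17, power 31%.

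The step 2 formula gives 57% and 31%.

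**5. No true effect.** Same design, covariate shifted by condition and correlated 0.2 to 0.5 with the outcome through a common cause. The adjusted coefficient is about -b x shift; for example, -0.5 x 0.26 = -0.13 (simulated -0.127). False positives rise from about 5% to 6.5-22% for a shift of 0.26 SD and 14-68% for 0.54 SD. The spurious effect runs against the covariate shift: a toolkit that only improves the covariate would look harmful on the outcome.

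**6. Does the fit criterion screen such covariates out?** Treating observations as independent, -n ln(1 - r^2) = 3.84 gives r = 0.046 for the 1,800 assessments in the protocol's Assessment Procedures, 0.055 for 1,260 (after 30% loss) and 0.103 for 360 cases. Nesting makes these approximate. A fit test in any case asks about association, not about when a variable was measured.

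**7. Is selection by fit itself the problem?** With ten baseline candidates chosen by deviance and no true effect, false positives were 3.9%, against 5.2% unadjusted (3,000 trials). A separate simulation with five and ten candidates gave 4.6% and 4.4%. No inflation appeared. What matters is the missing baseline limit.

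**The case against.** **No harmful covariate is named.** True. Comorbid symptoms and trauma history sit at the child level, where baseline values are the natural reading. The point is that the rules admit follow-up values, and for level-1 terms in D8c the wording calls for them.

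**D8c requires rationale as well as fit, and the textbook guidelines may restrict the choice.** The first is correct, so step 6 does not test the whole rule. The second cannot be checked from the documents; neither document states a restriction.

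**Provider completion measures are poor candidates for Hypotheses 1 and 2.** This stands. They come after the coded sessions, so using them as predictors would be strained. The child and caregiver measures carry the point.

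**How many of the 14 are outcome instruments?** A reader might merge the two outcome lists and count six. The lists conflict: D8c's names only the K-SADS-PL (child and caregiver) among the 14, and the SAP's names four. The point needs only that symptom scales are repeated.

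**Toolkit use.** D8a asks whether fidelity "was affected by access to the tablet and tablet use, a 2-level MLM (level-1 child; level-2 provider) will be used", and the SAP speaks of SPARK use. A reader might infer that use replaces condition, or enters beside it and absorbs its effect. The documents do not support that: D8a and D8b specify a condition term and no use term, and the SAP goes on to compare conditions. What remains is loose lead-in wording.

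**The magnitudes rest on assumed b and f.** They do, and below the break-even f the rule would help. No figure above estimates what this trial will lose.

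**Conclusion.** The point holds as a fault in the written rules. D8c directs unnamed time-varying covariates into the primary Hypothesis 3 model, and D8a and D8b admit covariates to the Hypothesis 1 and 2 models without limiting them to baseline. Neither the SAP nor the intention-to-treat statement withdraws this. If an admitted follow-up measure is changed by the toolkit, the condition effect is reduced to 1 - b x f of its value, or biased where there is no effect.

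The mechanism is certain; the size is not. With b of 0.3 to 0.5, f of 0.5 to 1 leaves 50% to 85% of the effect and 37% to 70% power, while f = 0 raises power to 84% to 90%. So even the direction of the power change is unknown. The power figures use a single-level approximation, checked by simulation only in the two-level setting with 120 providers. D8h states 400 providers; the share left does not depend on that number.

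Two stronger conclusions are not supported: that the plan lacks a randomised comparison, and that choosing baseline covariates by fit is itself harmful.

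**What to change.** 1. In D8c, delete the time-varying-covariate sentence from the primary Hypothesis 3 model. Keep any such model as a secondary, non-randomised analysis.
2. In D8a to D8c and SAP 2.9.1, limit covariates for Hypotheses 1 to 3 to case order and baseline (study-entry) child and provider variables. State that comorbid symptoms means the baseline value. A provider's second and third families enter after that provider has been randomised, so define a child's baseline as that family's own baseline assessment.
3. Preferably name the baseline covariates in advance. This is good practice rather than a correction of demonstrated harm.
4. Minor wording: in D8a, D8b and SAP 2.9.1, name randomised condition as what the Hypothesis 1 and 2 tests assess. Report the association with toolkit use as secondary, since D4e leaves use to the provider.

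The cost is wording only, with no new data. What is given up is the precision from any time-varying covariate that the toolkit does not affect: at b of 0.3 to 0.5, 84% to 90% power instead of 80%.

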D8d. Hypothesis 4 and 5: Provider fidelity (hypothesis 4 target) and child engagement (hypothesis 5 target) will mediate the relation between study condition and mental health outcomes. The proposed design is consistent with an enhancement mediation design¹³³ to determine if provider fidelity and child engagement are the mechanisms by which tablet-facilitated TF-CBT reduces psychopathology. Enhancement designs evaluate mediation by experimentally manipulating a variable that enhances the effect of the mediator when direct experimental control of the mediator is not possible.¹³⁴ These mechanistic hypotheses will be tested with established guidelines for multilevel mediation¹³¹. Significance is determined by a product of coefficients test with asymmetric bootstrapped SEs and 95% CIs for the product. This requires estimation of two paths: the effect of tablet-facilitated TF-CBT on engagement and fidelity (a-paths); and the effect of engagement and fidelity on outcomes, controlling for the effect of tablet TF-CBT (b-paths). The mediation effect is estimated by the product of the fixed effect coefficients for the a- and b-paths. A Monte Carlo method is used to create a 95% confidence interval to test for the mediated effect as this effect does not assume a normal distribution. Provider fidelity and child engagement will be evaluated in separate models. Tests for mediated effects are associated with a number of challenges and assumptions such that a single study typically cannot address and overcome each of them.¹³³⁻¹³⁴ As emphasized by MacKinnon and colleagues, the proposed randomized design is a relative strength that strengthens conclusions about the mediated effects. The mediation hypothesis will first be evaluated using all time points. If supported, follow-up analyses in which mechanism measures obtained from the first half of treatment will evaluate change in psychopathology in the second half of treatment. This two stage procedure will support the causal sequence of mediation - that an initial change in the mediator is associated with a reduction in psychopathology.¹³⁴ Combined, the proposed mediation model will provide important preliminary evidence to support, or reject, therapist fidelity and child engagement as potential mediators of the effect of iTF-CBT on child outcomes.

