**Quantitative Analyses Plan**

**NCT03305458**

**March 14, 2022**

### 2.9.1. Quantitative analyses

The RCT will enroll at least 120 providers who are expected to complete treatment with at least 3 child TF-CBT cases over the course of the project. This strategy results in a nested data structure in which cases ( $i$ ) are nested within providers ( $j$ ), which are nested within sites ( $k$ ). Hypotheses will be tested within a multilevel modeling framework (MLM) that accounts for several issues including: (1) dependency in outcomes due to the nesting; (2) multiple outcome distributions; (3) linear, non-linear, and/or piece-specific change patterns; (4) variable measurement points; and (5) missing observations. First, site-level variation will be evaluated to determine if there is systematic variability attributed to provider location. If there is evidence for significant between-site variability, then site will be added as additional level of analysis. However, if the amount of between-site variability is negligible, then the effects of site can be ignored. The benefit of removing site as an additional level is the increased power it affords to detect the primary effects of interest. The aims of the study do not include hypotheses for effects at the level of site. Separate models will be used for each variable described below. All subsequent models will be constructed according to the guidelines of Singer and Willett with respect to including fixed and random effects. Statistical significance will be determined with false discovery rate based on the number of tests conducted to account for multiple testing. To determine if provider fidelity is affected by overall SPARK use, a 2-level MLM (level-1 child; level-2 provider) will be used. Fidelity will be measured by the TF-CBT TPOCS-S. Providers' overall use of the toolkit will be calculated per child participant and averaged across toolkit content. Fidelity scores will be calculated per child participant such that each provider will have three ratings. An aggregate fidelity score will determine if there are differences across conditions (SPARK + TF-CBT vs. standard TF-CBT) while accounting for the nesting of providers. A similar approach will be used to evaluate the effect of SPARK use on child engagement. Response to the intervention will be evaluated with a piecewise longitudinal MLM that contains an additional level corresponding to time. Level-1 will correspond to time, level-2 to child, and level-3 to provider. The primary outcome will be scores on the CATS, CAT-Caregiver, CES-DC, and BPM. A piecewise model allows for separate change trajectories to be estimated for distinct periods of time. Patients are expected to show more rapid change during treatment than during follow-up (roughly corresponding to 9- and 12-month post-baseline period). Group comparisons will be made at level-3. Of interest is the cross-level interaction between rate of change during treatment and the condition to which the provider was assigned. Cross-level interactions between the rate of change during follow-up also will be examined. An enhancement mediation design will be used to determine if provider fidelity and child engagement are the mechanisms by which SPARK reduces symptomatology. Enhancement designs evaluate mediation by experimentally manipulating a variable that enhances the effect of the mediator when direct experimental control of the mediator is not possible. These mechanistic hypotheses will be tested with established guidelines for multilevel mediation. Significance is determined by a product of coefficients test with asymmetric bootstrapped standard errors and 95% confidence intervals for the product. This requires estimation of two paths: the effect of SPARK on engagement and fidelity (a-paths); and the effect of engagement and fidelity on outcomes, controlling for the effect of SPARK (b-paths). A Monte Carlo method is used to create a 95% confidence interval to test for the mediated effect as this effect does not assume a normal distribution. Provider fidelity and child engagement will be evaluated in separate models. The mediation hypothesis will first be evaluated using all time points. If supported, follow-up analyses in which mechanism measures

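### The H4/H5 mediation test controls the mediator-to-outcome path for study condition only, so a symptom-level analysis can show mediation that comes from case severity

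*Protocol*

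**What the plan says.** Protocol D8d tests the product of two coefficients. The a-path is the toolkit's effect on fidelity or engagement. The b-path is "the effect of engagement and fidelity on outcomes, controlling for the effect of tablet TF-CBT (b-paths". SAP 2.9.1 repeats this with the toolkit's new name: "the effect of engagement and fidelity on outcomes, controlling for the effect of SPARK (b-paths". Neither sentence names any other control.

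On the outcome, D8d says "The mediation hypothesis will first be evaluated using all time points" and does not state whether the b-path uses symptom level or rate of change. If that stage is positive, D8d plans "follow-up analyses in which mechanism measures obtained from the first half of treatment will evaluate change in psychopathology in the second half of treatment". The test is an interval: "A Monte Carlo method is used to create a 95% confidence interval to test for the mediated effect".

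The mediator is one value per child for the whole treatment. For engagement (D8b), "An aggregate CIRS score for each child will be used", and D8a treats fidelity the same way.

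Covariates appear elsewhere. D8a and D8b select child and provider covariates by model fit. In D8c, "The level-2 model will account for child level covariates, including comorbid symptoms and trauma history", and the time structure is given as "The level-1 model will include a fixed effect for pretreatment (intercept), rate of change during treatment". D8f adds provider experience and attitudes as exploratory moderators. None of these is said to carry into D8d. The SAP names no baseline covariates.

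D8d presents the randomised design as a relative strength for the mediation conclusions. It also warns that one study cannot meet every mediation assumption, and it calls the evidence preliminary. The SAP omits both the warning and the word preliminary.

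**The concern.** Providers are randomised to toolkit access. They are not randomised to a level of fidelity, nor children to a level of engagement. The a-path is therefore an experimental contrast, while the b-path is an observational association.

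The documents themselves make confounding of that association plausible. For H5, the negative items of the engagement scale cover withdrawal and avoidance in session (D4i), and avoidance is one of the PTSD symptom clusters required at entry (D4f). The mediator may partly record how ill the child was beforehand. For H4, D4h lets providers adapt the treatment components to a limited degree to the patient's needs, so measured fidelity can depend on how difficult the case is.

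If such an association exists, it is multiplied by the toolkit's effect on the mediator. H4 and H5 are declared hypotheses, and the trial's rationale is built on these two targets. A false positive would therefore support the wrong account of how the toolkit works.

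**Working it through.** **1. The plan's own figure.** D8h states 0.80 power for mediation at 0.26 on both paths. Read 0.26 as a standardised coefficient and take joint power = Φ(z_a − 1.96) × Φ(z_b − 1.96), with z_a = 0.26·√(n/(1 − 0.26²)) and z_b = 0.26·√n.

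| Children | Effective n | z_a | z_b | Joint power |
|---|---|---|---|---|
| 360, independent | 360 | 5.11 | 4.93 | 0.998 |
| 360, design effect 1 + 2 × 0.15 = 1.30 | 276.9 | 4.48 | 4.33 | 0.985 |
| 252 (30% dropout) | 252 | 4.27 | 4.13 | 0.975 |
| 252, design effect 1.30 | 193.8 | 3.75 | 3.62 | 0.917 |

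Power of 0.80 needs 148 independent children, or about 192 with the design effect, so the statement reproduces on this reading. If 0.26 were a standardised mean difference on the a-path, joint power would be 0.69 (360, independent) down to 0.42 (252, design effect). Neither figure bears on bias: a test with power to find b also has power to find a confounded b.

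**2. Size of the bias when the true b is 0.** Assume a correlation of −ρ between baseline severity and the mediator, and 0.5 between assessments. Both are assumptions. Negative b is favourable. Consider two cases: (A) the measured baseline score carries all the confounding; (B) an underlying severity carries it, and the baseline score measures that severity imperfectly.

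| b-path outcome | Bias in A | Bias in B |
|---|---|---|
| Post-baseline level, condition only | −0.5ρ | −ρ |
| Mean of all five assessments, condition only | −(ρ + 4 × 0.5ρ)/5 = −0.6ρ | −ρ |
| Post-baseline level, adjusted for baseline | 0 | −(ρ − 0.5ρ)/(1 − ρ²) ≈ −0.5ρ |
| Change from baseline, condition only | −0.5ρ + ρ = +0.5ρ | −ρ + ρ = 0 |

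At ρ = 0.2 the first row gives −0.10 (A) and −0.20 (B); simulation gave −0.105 and −0.209. Baseline adjustment in B gives −0.104 by formula and about −0.11 by simulation.

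**3. False mediation rates.** Simulation used 120 providers × 3 children, ICC 0.15, 2,000 trials per setting, Monte Carlo 95% interval, true b = 0 and no direct effect. The 120 comes from the SAP and from 60 per arm in D1, and 120 × 3 = 360; the protocol's 400 × 3 would be 1,200. Toolkit effects were 0.34 SD (the detectable effect in D8h) and 0.52 SD (0.26 per SD of a 1:1 indicator, 0.26/0.5). The table gives the percentage of trials with a significant favourable indirect effect.

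| Outcome and adjustment | Toolkit effect | ρ = 0.1 | ρ = 0.2 | ρ = 0.3 |
|---|---|---|---|---|
| Level, all five, condition only (A to B) | 0.34 | 22–54 | 71–85 | about 80 |
| Level, all five, condition only (A to B) | 0.52 | 32–72 | 87–99 | 98–99 |
| Post-baseline level, baseline-adjusted, A | 0.52 | 4 | 3 | 2 |
| Post-baseline level, baseline-adjusted, B | 0.52 | 38 | 90 | 99 |

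A separate simulation with one noisier post-treatment score per child (600 replicates, 0.34 SD, all confounding through measured baseline) gave 11%, 36% and 65%, falling to 3–4% after baseline adjustment.

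**4. Conditions that change the answer.**
- No toolkit effect on the mediator: false mediation is at most about 6% in total, because a is null.
- Slope outcome, parallel courses: about 2–3% favourable in B; in A the bias reverses, with 12–70% significant in the adverse direction at 0.52 SD.
- Slope outcome, less ill children also recovering faster (0.52 SD, ρ = 0.2 and 0.3): 80–98% favourable in B, about 2% in A.
- Baseline dropped from a level outcome, condition only (ρ = 0.2, 0.52 SD): still 68% (A) to 99% (B).
- Passing both stages: at most 3% with parallel courses; 4–14% if less ill children recover faster.

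**The case against.** The strongest reply is that the outcome model may well be the D8c growth model. That model has a pre-treatment intercept, and D8d speaks of change in psychopathology. On a change outcome the assumptions that produce false mediation for a level outcome can instead hide true mediation. This stands: the direction of the error depends on a choice that neither document states. It does not remove the point, because the bias returns in case B if less ill children also improve faster.

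The second stage is a real safeguard and keeps full false support low in these settings. It runs only after a positive first stage, names no baseline adjustment, and does not withdraw the first-stage result. D8d's own caveats also count in the plan's favour, though they do not name confounding and the SAP drops them.

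A reader might infer that using all time points, baseline included, is what creates the problem. The documents do not expressly say that baseline enters the b-path outcome, and leaving it out barely helps; the missing adjustment is what matters. A reader might also infer that baseline and provider covariates appear nowhere in the plan. They do, in D8a–D8c and D8f; the gap is that their use in D8d is unstated.

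**Conclusion.** The point holds in a conditional form. As written, a symptom-level b-path adjusted for condition alone can produce a significant first-stage indirect effect with no mechanism behind it, provided the toolkit moves the mediator and case severity is related to it. The first condition is what H1 and H2 predict, so the risk arises when the toolkit succeeds on its targets.

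At a 0.34 SD toolkit effect the illustrative false-positive rate is 22–54% for a correlation of 0.1 and 71–85% for 0.2. These rates rest on assumed correlations, 120 providers and a level outcome; they are not predictions for this trial. The numerical example is most natural for engagement. For fidelity it depends on providers adapting delivery to the case.

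Two stronger conclusions are not supported. The documents do not show that the mediation result will be false, since a change outcome can remove or reverse the bias. Nor would baseline adjustment settle the matter: it restores rates of about 2–4% only if the measured baseline carries all the confounding, and otherwise about halves the bias. This should be fixed, but it does not threaten the trial: H1–H3 are unaffected.

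**What to change.** In D8d and SAP 2.9.1:

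1. State the b-path outcome as post-baseline symptom level, adjusted for the baseline value of that same outcome.
2. Put the same pre-treatment variables in the a-path and b-path models: at least baseline symptom score, child age and trauma history. Further candidates already in the measures lists are baseline caregiver distress (K6, CESD-R) and provider experience and attitudes at entry (EBPAS).
3. Apply the same baseline adjustment to the second-stage test.
4. Add a sensitivity analysis showing how large a residual mediator–outcome correlation would remove the indirect effect.
5. Replace the sentence on the strength of the randomised design with: *randomisation identifies the a-path; the b-path is observational, adjusted for measured baseline covariates, and residual confounding is possible.*

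The cost is wording in two documents, slightly larger models and one sensitivity analysis, with no new data collection. The reported mediated effect may be smaller.
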